- To determine the lowest effective dose of Increlex® defined as the cut-off dose under which there is no further effect on the height velocity anymore (short-term evaluation: 1-year height velocity);
- To assess quality of life (QoL) during Increlex® therapy and in the post-treatment period (using EQ-5D version EQ-5D-Y (paediatric questionnaire));
- To describe the timeframe of the occurrence of neoplasia (benign and malignant) and hypoglycaemia.

Registry Design

This is a multicentre, global, prospective, non-interventional, observational, open-ended, post-authorisation safety surveillance registry designed to collect safety and effectiveness data on the use of Increlex® in children and adolescents with SPIGFD. Data on treatment exposure, compliance and QoL of participants will also be collected.

The objective is to screen all Increlex®-treated patients with SPIGFD at each participating site of the participating countries with the aim of enrolling as many patients as possible.

The decision to prescribe Increlex® will be made prior to and independently of the decision to enrol the patient in the registry. Treatment with Increlex® should be directed by physicians who are experienced in the diagnosis and management of patients with growth disorders. The dose should be individualised for each participant according to the locally approved product information. The data collected for a participant will be those that exist in their medical records as part of standard medical care except for additional QoL assessments and post-treatment safety follow-up in the context of fulfilling the Specific Obligation (SO2). Data will be collected utilising an electronic Case Report Form (eCRF) via the internet.

The date of the inclusion visit is not determined by the protocol. Patients who have started Increlex® treatment before the implementation of the registry in their country may also be enrolled. Data will be then retrospectively collected in the eCRF.

During the first visit, the Investigator will check the patient's eligibility according to the inclusion and exclusion criteria and must obtain written informed consent before any further data collection.

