It is intended to collect safety data in children and adolescents receiving Increlex® therapy for SPIGFD according to the locally approved product information at sites experienced in the diagnosis and management of children and adolescents with SPIGFD.

The aim is to enrol as many Increlex®-treated patients as possible into the registry at each participating site and the results should provide valuable information on the long-term risk of malignancies and other risks in a relatively large group of children and adolescents with this rare disease.

To be eligible for enrolment in the registry, participants must comply with all of the following inclusion and exclusion criteria:

Inclusion Criteria

- (1) Children and adolescents from 2 to 18 years:
 - For US, patients starting or planning to start or currently receiving treatment with Increlex® therapy for severe primary IGF-1 deficiency as defined by the US Increlex® prescribing information or for growth hormone (GH) gene deletion who have developed neutralizing antibodies to GH.
 - For EU, patients starting or planning to start or currently receiving treatment with Increlex® therapy according to the locally approved product information. Note: not applicable for patients enrolled in the EU-IGFD registry and entering or currently in the post-treatment period.
- (2) Signed informed consent as per local regulations needs to be obtained. Parents or legally authorised representatives if applicable must give signed informed consent before any registry-related activities are conducted. Assent from the participant should also be obtained as appropriate.

Exclusion Criteria

- (1) Patient currently participating in an Increlex® clinical trial.
- (2) Patient currently participating in any clinical trial for growth retardation.
- (3) Patient with any contraindication to Increlex® or any condition subject to special warning as per the locally approved label.
 - For US patients, these include patients with hypersensitivity to the active substance or any of the excipients, patients with active or suspected neoplasia and patients with closed epiphyses.

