The same analyses will be performed in a subset of children and adolescents exposed to Increlex® for at least 3 years.

Post-treatment AE listings will be presented by participant, primary SOC and PT.

An overall summary table of special situations occurring during the treatment and post-treatment periods will be presented with the number and proportion of participants and the number of events. For the post-treatment period, the same analyses will be performed in a subset of children and adolescents exposed to Increlex® for at least 3 years.

Concomitant medications during the treatment and post-treatment periods will be tabulated.

Incidence of neoplasia (benign and malignant) and hypoglycaemia will be presented according to the timeframe of occurrence (e.g. within the first 3 years after start of treatment, between 3 and 5 years and over 5 years).

All secondary safety data will also be included in the participant data listings.

Effectiveness Analyses

Effectiveness analyses will be based on the Registry Population.

The raw values of the following effectiveness parameters will be described at different timepoints (every 6 months from the start of treatment) as well as the change from baseline: height SDS, height velocity, body mass index (BMI) SDS, bone age development, pubertal stage.

For participants who reached the FAH, the estimation of the difference between the PAH and the FAH will be presented.

Main effectiveness parameters (height SDS, height velocity) will be described according to average dose received over the course of the study and according to dose ranges (e.g. 4 dose ranges (≤ 50 , $]50-80]$, $]80-110]$, $> 110 \mu\text{g/kg BID}$)). This analysis will support the description of the lowest effective dose.

Multivariate linear regression analyses will be used to identify predictive factors of height SDS change, height velocity, bone age development after 1 year of treatment or more. The same method will be used to assess the predictive factors of FAH.

The Cox regression model including covariates as sex, age or height SDS at start of Increlex® will be used to estimate the time from start of treatment to reach the puberty for a subset of prepubertal patients at start of Increlex®.

Biological assessments (IGF-1, IGFBP3), raw values and change from baseline, will be described at different timepoints.

Exposure to Increlex® Therapy

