9 RESEARCH METHODS

9.1 Registry Design

This is a multicentre, global, prospective, non-interventional, observational, open-ended, post-authorisation safety surveillance registry designed to collect safety and effectiveness data on the use of Increlex® in children and adolescents with SPIGFD. Data on treatment exposure, compliance and QoL of participants will also be collected.

The objective is to screen all Increlex®-treated patients with SPIGFD at each participating site of the participating countries with the aim of enrolling as many patients as possible.

The decision to prescribe Increlex® will be made prior to and independently of the decision to enrol the patient in the registry. Treatment with Increlex® should be directed by physicians who are experienced in the diagnosis and management of patients with growth disorders. The dose should be individualised for each participant according to the locally approved product information. The data collected for a participant will be those that exist in their medical records as part of standard medical care except for additional QoL assessments and post-treatment safety follow-up in the context of fulfilling the Specific Obligation (SO2). Data will be collected utilising an electronic Case Report Form (eCRF) via the internet.

The date of the inclusion visit is not determined by the protocol. Patients who have started Increlex® treatment before the implementation of the registry in their country may also be enrolled. Data will be then retrospectively collected in the eCRF.

During the first visit, the Investigator will check the patient's eligibility according to the inclusion and exclusion criteria and must obtain written informed consent before any further data collection.

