Effectiveness analyses will be based on the Registry Population.

The raw values of the following effectiveness parameters will be described at different timepoints (every 6 months from the start of treatment) as well as the change from baseline: height SDS, height velocity, BMI SDS, bone age development, pubertal stage.

For participants who reached the FAH, the estimation of the difference between the PAH and the FAH will be presented.

Main effectiveness parameters (height SDS, height velocity) will be described according to average dose received over the course of the study and according to dose ranges (e.g. 4 dose ranges (≤ 50 , $]50-80]$, $]80-110]$, $> 110 \mu\text{g/kg BID}$)). This analysis will support the description of the lowest effective dose.

Multivariate linear regression analyses will be used to identify predictive factors of height SDS change, height velocity, bone age development after 1 year of treatment or more. The same method will be used to assess the predictive factors of FAH.

The Cox regression model including covariates as sex, age or height SDS at start of Increlex® will be used to estimate the time from start of treatment to reach the puberty for a subset of prepubertal patients at start of Increlex®.

Biological assessments (IGF-1, IGFBP3), raw values and change from baseline, will be described at different timepoints.

Exposure to Increlex® Therapy

The treatment duration as well as the dose of Increlex® at each timepoint (initiation, 3 months, 6 months, 1 year, and every 6 months thereafter) will be described.

Duration of post-treatment follow-up will also be summarised.

Quality of Life Analysis

The QoL of participants aged 4 and over will be assessed using the EQ-5D-Y paediatric questionnaire (see Section 9.3.2.5 for details).

The 5 dimensions/domains (mobility; looking after myself; doing usual activities; having pain or discomfort; feeling worried, sad or unhappy) will be described at each timepoint as well as the evolution from baseline. The VAS will be described as a quantitative parameter at each timepoint as well as the change from baseline.

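### Children enrolled while already on Increlex bring back-filled data from first dose, yet could enrol only if still treated with open epiphyses: early growth is likely overstated if poor responders stopped first, and puberty likely dated late where enrolment came long after first dose

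*Protocol*

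**What the plan says.** The Abstract (Registry Design) states: "Patients who have started Increlex® treatment before the implementation of the registry in their country may also be enrolled". Section 9.1 repeats this and adds: "Data will be then retrospectively collected in the eCRF". The date of the inclusion visit is left open.

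Entry depends on treatment status at that visit. The EU inclusion criterion admits "patients starting or planning to start or currently receiving treatment with Increlex® therapy according to the locally approved product information", and the US criterion names the same three states. The US exclusions include "patients with active or suspected neoplasia and patients with closed epiphyses", and the EU exclusions also name closed epiphyses. The exception for the post-treatment period covers only patients already enrolled in the EU-IGFD registry.

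Section 9.7.2.6 sets the analysis: "Effectiveness analyses will be based on the Registry Population". Height SDS, height velocity and the other parameters are "described at different timepoints (every 6 months from the start of treatment) as well as the change from baseline". The Cox model "will be used to estimate the time from start of treatment to reach the puberty for a subset of prepubertal patients at start of Increlex". Neither part separates children enrolled at first dose from those enrolled later, and the subgroup examples in 9.7.3 do not mention enrolment timing.

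Checklist item 7.2.1 marks selection bias as not applicable, while item 12.1.1 says that section 9.9 discusses it. Section 9.9 covers missing pre-treatment measurements, variation between sites and the non-randomised dose, but not selection on continued treatment.

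**The concern.** Consider two children who start on the same day, before a site opens. One grows well and is still treated when the site opens three years later. That child enrols and contributes to the 6-month, 1-year, 2-year and 3-year results as far as the records allow. The other stops after eighteen months for lack of effectiveness, which is a listed stopping reason, and cannot enrol under the current criteria. The early results then come from persisters only. Methods for missing data do not help, because the second child has no record.

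The puberty model has a related weakness. Its clock starts at first dose, but a child enrolled late is observed only because he or she was still treated, under 18 and with open epiphyses at enrolment. Children who matured early relative to first dose are under-represented.

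At stake are the early height SDS and velocity results, the predictor models, the puberty estimate and the lowest-effective-dose objective, whose short-term measure is 1-year height velocity.

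**Working it through.** The plan states no figure on this point, so there is none to reproduce. The checks below use the protocol's own dates and pivotal-study result. Everything else is an assumption, marked as such.

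**1. How long can the gap be?** From dates in sections 6, 5 and 7.2:
- Original EU countries: authorisation August 2007, registry start 9 December 2008, so about 1.4 years of possible treatment before the registry opened.
- USA: authorisation August 2005, global expansion (Amendment 6) 10 July 2020, so about 14.9 years. This is an outer bound, since the child must still be treated and of eligible age.

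**2. Growth, persistence model.** Year-1 velocity is taken as normal with mean 8.0 and SD 2.3 cm/year (pivotal study, section 7.2). With z the standardised velocity:
- P(still treated | z) = 1 / (1 + exp(−(a + ln(OR)·z))), with a set to give the assumed overall persistence P.
- Mean among persisters = 8.0 + 2.3 × E[z·P(still treated | z)] / P.
- Pooled bias = share already treated at entry × (mean among persisters − 8.0), with the share assumed to be 50%.

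| Persistence (assumed) | OR per SD (assumed) | Mean among persisters | Pooled bias, cm/year |
|---|---|---|---|
| 40% | 1.5 / 2 / 3 | 8.54 / 8.86 / 9.22 | +0.27 / +0.43 / +0.61 |
| 60% | 1.5 / 2 / 3 | 8.36 / 8.58 / 8.81 | +0.18 / +0.29 / +0.41 |
| 80% | 1.5 / 2 / 3 | 8.18 / 8.30 / 8.43 | +0.09 / +0.15 / +0.21 |

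An OR of 1 gives zero bias. For scale, the 95% half-width of the mean at an assumed n = 300 is 1.96 × 2.3 / √300 = 0.26 cm/year. Five of the nine cells exceed it and four do not. At n = 100 the half-width is 1.96 × 2.3 / √100 = 0.45, and only one cell exceeds it.

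**3. Growth, hazard model.** As a second view, assume a stopping hazard of 5% or 15% per year after year 1, raised 1.5 or 2 times per SD of poorer response, and a gap uniform from zero to the stated maximum.

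| Maximum gap | Bias among children already treated at entry, cm/year |
|---|---|
| 1.36 years | at most 0.02 |
| 5 years | 0.08 to 0.32 |
| 10 years | 0.17 to 0.62 |

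With 25% to 75% of the cohort already treated at entry, the 10-year row becomes 0.04 to 0.47 in the pooled mean. With a hazard ratio of 1 the bias is zero, apart from simulation noise.

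**4. Puberty.** Assume age at first dose uniform on 3 to 10 years, age at puberty normal (12, 1.2), closure about 4 years after puberty, and other stopping at 0 or 10% per year (multiplied by 1, 2 or 4 after puberty). Entry requires ongoing treatment, age under 18 and open epiphyses. All children in this simulation start before enrolment, so a mixed cohort would shift less. The true median from first dose is about 5.5 years.

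| Maximum gap | Median too late, clock from first dose without delayed entry |
|---|---|
| 1.36 years | 0.00 years |
| 5 years | 0.01 to 0.13 |
| 10 years | 0.29 to 0.51 |
| 15 years | 0.44 to 0.69 |

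With the same clock but risk sets entered at enrolment, the median is within about 0.04 years of the true value in every scenario.

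**The case against.** Several counter-arguments have weight.

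- **Stopping need not depend on growth.** Section 9.3.2.4 lists eleven reasons. Several, such as insurance, change of physician, product shortage and COVID-19, need not relate to response. This stands: the growth bias is likely, not proven.
- **The entry rule is the current one.** Participants from before Amendment 6 (July 2020) entered under criteria not shown, so nothing can be said about how they were selected.
- **Back-filling will be incomplete.** Section 9.9 warns that pre-treatment height, velocity and pubertal stage may be missing, so some late enrollees will drop out of change from baseline or the prepubertal subset. This reduces their share but does not remove the selection among those who remain.
- **Closure is not onset of puberty.** A pubertal child still treated with open epiphyses can enrol. The shift is therefore small unless gaps are long.
- **The analysis plan could deal with it.** Delayed entry uses the same time scale, so the protocol does not forbid it. But the protocol does fix the population and the time origin, and its checklist declares selection bias not applicable. Followed as written, it pools the two kinds of participant.
- **Effectiveness is secondary and descriptive**, and section 9.9 already doubts that the lowest effective dose can be determined. This limits the stakes.

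A reader might infer that the bias is as large as the confidence interval or larger. The documents do not support that: the share already treated, the stopping rates and the sample size are all unknown, and four of the nine scenarios fall below the half-width even at n = 300. A reader might also infer that the main analysis should be confined to children enrolled within a few weeks or months of first dose. In a disease rarer than 1 in 100,000 that is a trade-off, not a necessity.

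**Conclusion.** The concern holds in direction and under conditions; its size cannot be derived. For participants enrolled under the current criteria, the plan pools early data selected on continued treatment with data from children followed from first dose. Year-1 velocity is likely overstated to the extent that poor responders stopped before enrolment. Under 40% to 80% persistence, OR 1.5 to 3 per SD and 50% already treated at entry, the illustration gives about +0.1 to +0.6 cm/year. It is zero if stopping is unrelated to response, and negligible for children in the original EU countries whose gap was at most about 1.4 years. Time to puberty is likely late where gaps are long, by roughly 0.3 to 0.7 years with assumed gaps of up to 10 to 15 years and little with gaps of up to 5. The issue therefore matters mainly for countries added late. The checklist answer that selection bias does not apply is wrong on the protocol's own design.

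**What to change.** In 9.7.2.6 and the Abstract:

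- Keep the Registry Population, but present the growth tables, including 1-year height velocity by dose range, separately for participants enrolled at or near first dose (window to be fixed in advance) and those enrolled later.
- Repeat the regression models in the first group as a sensitivity analysis.
- In the Cox model keep the clock from first dose, but let each participant enter the risk set at enrolment (left truncation).

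In 9.9, describe the selection on continued treatment and open epiphyses. Correct checklist item 7.2.1 so that it agrees with item 12.1.1 and the revised 9.9.

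First-dose date and enrolment visit date are already collected, so no new data are needed. The cost is one extra table column, wider intervals within each group, and fewer events in the Cox model, because puberty reached before enrolment no longer counts.

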5 AMENDMENTS AND UPDATES

The current version of the protocol was released on 18 September 2025 and includes protocol amendments 1 to 9. For all protocol amendments, amendment forms were prepared and are provided in Appendix 1.

Amendment Number	Release Date	Section of protocol (Amendment Form)	Amendment or update	Reason
1	07 October 2008	Appendix 1	Non-substantial; eCRF, local ICF, database and SAP update	Removal of the ethnic origin, requested by CNIL
2	11 February 2009	Appendix 1	Substantial; eCRF, local ICF, database and SAP update	Addition of Final Adult Height requested by the HAS. Version for ALL countries except for France.
3	18 December 2015	Appendix 1	Substantial; eCRF, local ICF, database and SAP update	To answer the commitment request of the EMA, i.e. to collect safety information 2 and 5 years after the end of Increlex® therapy in the subjects who have been exposed for at least 3 years, irrespective of final height.
4	04 August 2016	Appendix 1	Non-substantial; no update to eCRF, local ICF, database or SAP	To add references to the Good Pharmacovigilance Practice and Good Pharmacoepidemiology Practice Guidelines
5	08 January 2018	Appendix 1	Substantial; eCRF, local ICF, database and SAP update	Register 100% of patient taking Increlex® in participating centres, without recording any medical or private information without ICF signature and/or subject agreement. Remove Greece as participating country as no subjects have been included since the start of the study. Add a clarification regarding date of birth collection: 
Remove day of birth date will increase subject data privacy. The recording 01 for the day of birth is a convention to facilitate data collection.Keeping months in the birth date is mandatory for optimal SDS calculations.
6	10 July 2020	Appendix 1	Substantial; eCRF, local ICF, database and SAP update	Geographic expansion of the EU-IGFD registry to additional countries within and outside Europe where the product is registered and marketed (i.e. conversion into a global registry), with long-term follow-up for all children and adolescents treated with Increlex® to fulfil the EMA Specific Obligation (SO2) 002.1 to investigate long-term safety after the end of Increlex® treatment, regardless of treatment duration, and the possible occurrence of malignancies as well as other risks.
7	08 February 2021	Appendix 1	Substantial; SAP update	Update of secondary objectives: to include data collection of the Increlex® (or mecasermin) doses as a secondary objective of the global registry to allow for potential further descriptive analyses.

Amendment Number	Release Date	Section of protocol (Amendment Form)	Amendment or update	Reason
8	19 April 2021	Appendix 1	Non-substantial, SAP update	Modification of secondary objective related to the determination of lowest effective dose Precisions on participating countries Update of the off-label patients follow-up
9	18 September 2025	Appendix 1	Substantial	Change of sponsor

CNIL = *Commission nationale de l'informatique et des libertés*; eCRF = electronic Case Report Form; EMA = European Medicines Agency; EU-IGFD = European Increlex® (Mecasermin [rDNA Origin] Injection) Growth Forum Database; HAS = *Haute Autorité de Santé*; ICF = informed consent form; SAP = Statistical Analysis Plan; SDS = standard deviation score.

6 MILESTONES

Milestone	Date
Start of data collection (registry initiation date)	09 December 2008
Start of data collection under Protocol Amendment #8	Planned Q2 2021
End of data collection	N/A (ongoing open-ended registry)
Registration in the ENCePP register	17 October 2014
Interim CSR 1	01 December 2011
Interim CSR 2	22 November 2013
Interim CSR 3	14 December 2015
Interim CSR 4	20 December 2017
Interim CSR 5	10 January 2020
Interim CSR 6	Planned December 2021
Final report of registry results	N/A (ongoing open-ended registry)

CSR = Clinical Study Report; ENCePP = European Network of Centres for Pharmacoepidemiology and Pharmacovigilance; N/A = not applicable; Q = quarter.

